3.3. Study Treatments

This study will enroll approximately 20 participants (Primary Cohort). After GDRC review (Section 5.1.3), an optional Pilot Cohort of up to 20 additional participants may be added.

Participants in the Primary Cohort and in the optional Pilot Cohort will be randomized in a 1:1 ratio to one of the following 2 treatment groups based on the dose of GS-2872 as follows:

Treatment Group 1:

Oral LEN for loading 600 mg followed by LEN 927 mg SC on Day 1; oral LEN for loading 600 mg on Day 2

GS-5423 30 mg/kg, administered via IV infusion over 60 minutes on Day 1 (after LEN SC injection)

GS-2872 10 mg/kg, administered via IV infusion over 60 minutes on Day 1 (after GS-5423 infusion)

Treatment Group 2:

Oral LEN for loading 600 mg followed by LEN 927 mg SC on Day 1; oral LEN for loading 600 mg on Day 2

GS-5423 30 mg/kg, administered via IV infusion over 60 minutes on Day 1 (after LEN SC injection)

GS-2872 30 mg/kg, administered via IV infusion over 60 minutes on Day 1 (after GS-5423 infusion)

There is no stratification for randomization for the Primary Cohort.

For the optional Pilot Cohort, randomization will be stratified by the antibody (GS-5423 or GS-2872) to which the participant is sensitive.

All participants will discontinue their background oral ARV regimen 1 day prior to receiving study drugs on Day 1.

At Week 26, all participants will resume their baseline regimen of once daily oral ART (or compatible regimen selected by the investigator) and return to the clinic for visits at Weeks 38 and 52.

Unblinded treatment assignments will be provided to the investigators after all participants are back on their baseline ARVs (or compatible regimen selected by the investigator) at Week 26 or have discontinued the study, and the Week 26 analysis has been completed.

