4.2. Inclusion Criteria

Participants must meet all of the following inclusion criteria to be eligible for participation in this study:

- 1) The ability to understand and sign a written informed consent form (ICF), which must be obtained prior to initiation of study procedures;
- 2) Between 18 and 65 years of age, inclusive, at screening;
- 3) Plasma HIV-1 RNA < 50 copies/mL at screening;
- 4) On first-line ART for ≥ 2 years prior to screening. A change in ART regimen ≥ 28 days prior to screening for reasons other than virologic failure (VF) (eg, tolerability, simplification, drug-drug interaction profile) is allowed;
- 5) Documented plasma HIV-1 RNA < 50 copies/mL for ≥ 18 months preceding the screening visit (or undetectable HIV-1 RNA level according to the local assay being used if the limit of detection is ≥ 50 copies/mL). Unconfirmed virologic elevations of ≥ 50 copies/mL (transient detectable viremia, or “blip”) prior to screening are acceptable;
- 6) Proviral phenotypic sensitivity to both GS-5423 and GS-2872 at screening by the PhenoSense mAb Assay (Monogram Biosciences) for inclusion in the Primary Cohort; sensitivity at screening by the PhenoSense mAb Assay (Monogram Biosciences) to 1 mAb, either GS-5423 or GS-2872, within 18 months prior to enrollment for inclusion in the optional Pilot Cohort
 - In both cohorts, GS-5423 sensitivity is defined as 90% inhibitory concentration (IC_{90}) ≤ 2 μ g/mL; GS-2872 sensitivity is defined as $IC_{90} \leq 2$ μ g/mL;
- 7) CD4+ count nadir ≥ 350 cells/ μ L;
- 8) Screening CD4+ count ≥ 500 cells/ μ L;

- 9) Availability of a fully active alternative ART regimen, in the opinion of the investigator, in the event of discontinuation of the current ART regimen with development of resistance;
- 10) Normal ECG (if abnormal, determined by the investigator to be not clinically significant);
- 11) Adequate renal function:

Estimated glomerular filtration rate (eGFR) ≥ 70 mL/min according to the Cockcroft-Gault formula {[Cockcroft 1976](#)}:

$$\text{Male: } \frac{(140 - \text{age in years}) \times (\text{weight in kg})}{72 \times (\text{serum creatinine in mg/dL})} = \text{CL}_{\text{cr}} \text{ (mL/min)}$$

$$\text{Female: } \frac{(140 - \text{age in years}) \times (\text{weight in kg})}{72 \times (\text{serum creatinine in mg/dL})} \times 0.85 = \text{CL}_{\text{cr}} \text{ (mL/min)}$$

where, CL_{cr} = creatinine clearance;

- 12) Alanine aminotransferase (ALT) and AST $\leq 5 \times$ upper limit of normal (ULN);

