5.4. Prior and Concomitant Medications

Clinical data indicate LEN is a substrate of P-glycoprotein (P-gp) transporters, and an inhibitor of cytochrome P450 enzyme (CYP) 3A enzymes (moderate), breast cancer resistance protein (BCRP), and P-gp transporters. In vitro data suggest LEN is also a substrate of CYP3A and uridine diphosphate glucuronosyltransferase 1A1 (UGT1A1) enzymes. Concomitant use of LEN with some medications or herbal/natural supplements that are inhibitors or inducers of CYP3A, UGT1A1, or P-gp may result in increased or decreased LEN exposure, respectively. Concomitant use of LEN with some medications or herbal/natural supplements that are substrates of CYP3A, P-gp, or BCRP may result in increased exposure of these medications.

Representative medications listed in [Table 5-2](#) and herbal/natural supplements are currently excluded or should be used with caution while participating in this study; this table is not exhaustive. Any medication that is not on the list should be reviewed by Gilead prior to screening and throughout the study. Vitamins, acetaminophen, ibuprofen, and hormonal medications are allowed during the study period. Participants should discontinue disallowed concomitant medications 30 days prior to initiation of study drug, unless otherwise specified.

Vaccinations should not be administered within 14 days prior to infusion of GS-5423 and GS-2872 at Day 1.

Table 5-2. List of Representative Medications that are Prohibited or To Be Used with Caution due to the Potential for Drug-Drug Interaction with LEN

Medication Class	Prohibited Medications	Use Discouraged and To Be Used With Caution
Anticoagulants	—	Dabigatran etexilate: monitoring and/or dose reduction may be needed for certain populations per prescribing information
Anticonvulsants	Carbamazepine, oxcarbazepine, phenobarbital, phenytoin	—
Antimycobacterials	Rifampin, rifabutin, rifapentine	—
Antiretroviral agents	Any ARV not part of the study treatment regimen	—
Digoxin	—	Digoxin: concomitant use may result in increased levels of digoxin; use with caution and with appropriate monitoring of serum digoxin levels
Ergot derivatives	Ergotamine, ergonovine, dihydroergotamine, methylergonovine, ergometrine	—
Herbal/natural supplements	St. John's wort, echinacea, milk thistle (ie, silymarin), Chinese herb sho-saiko-to (or Xiao-Shai-Hu-Tang)	—

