3. GENERAL CONSIDERATIONS FOR DATA ANALYSES

Analysis results will be presented using descriptive statistics. For categorical variables, the number and percentage of participants in each category will be presented; for continuous variables, the number of participants (n), mean, standard deviation (SD) or standard error (SE), median, first quartile (Q1), third quartile (Q3), minimum, and maximum will be presented.

By-participant listings will be presented for all participants in the All Randomized Analysis Set and sorted by participant identification (ID) number, visit date, and time (if applicable). Data collected on log forms, such as AEs, will be presented in chronological order within the participant. The treatment group to which participants were randomized will be used in the listings. Age, sex at birth, race, and ethnicity will be included in the listings, as space permits.

There are the following 2 sets of analyses defined for this study. Data included in each analysis are defined as follows:

Long Acting (LA) Regimen Period Analysis

Long-acting (LA) Regimen Period Analysis includes efficacy (ie, HIV-1 RNA and CD4 cell count and percentage) and safety data collected during **Long Acting Regimen Period** from participants randomized and received at least one dose of the complete long acting study drug regimen (ie, SC LEN + GS-5423 and GS-2872) up to ART restart (eg, Week 26). All data collected up to the last exposure date of LA regimen (defined in Section 3.8.1) will be summarized except for data on AEs, death and concomitant medications. For AEs, death and concomitant medications, only data collected prior to the last exposure date of LA regimen will be included. For participants who did not restart ART on or before last study date or have missing ARV restart date, all data will be included.

Data included in this analysis will be used to assess the efficacy and safety data collected during the LA regimen period of the study. Results will be summarized by treatment group and overall.

Whole Study Period Analysis

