6.1.2. FDA-defined Snapshot Algorithm

The analysis window at Week 26 is defined as from Study Day 176 to Study Day 224, inclusive. All HIV-1 RNA data collected on-treatment (ie, data collected up to the earliest date of (196 days [28 weeks] after the dose date of complete long acting regimen, date of restarting ART) will be used in the US FDA-defined snapshot algorithm {[U. S. Department of Health and Human Services 2015](#)}. Virologic outcome will be defined as the following categories:

- HIV-1 RNA < 50 copies/mL: this includes participants who have the last available on-treatment HIV-1 RNA < 50 copies/mL in the Week 26 analysis window
- HIV-1 RNA ≥ 50 copies/mL: this includes participants
 - a) Who have the last available on-treatment HIV-1 RNA ≥ 50 copies/mL in the Week 26 analysis window, or
 - b) Who do not have on-treatment HIV-1 RNA data in the Week 26 analysis window and
 - i) discontinue study drug prior to or in the Week 26 analysis window due to lack of efficacy, or
 - ii) discontinue study drug prior to or in the Week 26 analysis window due to AE or death and have the last available on-treatment HIV-1 RNA ≥ 50 copies/mL, or
 - iii) discontinue study drug prior to or in the Week 26 analysis window due to reasons other than AE, death, or lack of efficacy and have the last available on-treatment HIV-1 RNA ≥ 50 copies/mL.

- No Virologic Data in the Week 26 Window: this includes participants who do not have on-treatment HIV-1 RNA data in the Week 26 analysis window because of the following:
 - a) Discontinuation of study drug prior to or in the Week 26 analysis window due to AE or death and the last available on-treatment HIV-1 RNA < 50 copies/mL, or
 - b) Discontinuation of study drug prior to or in the Week 26 analysis window due to reasons other than AE, death, or lack of efficacy and the last available on-treatment HIV-1 RNA < 50 copies/mL or,
 - c) Missing data during the window but on study drug.

The flowchart of the US FDA-defined snapshot algorithm is provided in [Appendix 2](#).

The Week 26 virologic outcomes for the US FDA-defined snapshot algorithm will be flagged in the listings.

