7.4.1. Nonstudy Drug Antiretroviral Medications

Any nonstudy drug ARV medications used prior to, during, or after the study (if collected) will be listed. No inferential statistics will be provided.

Antiretroviral medications at baseline will be summarized by ARV category and drug name. Antiretroviral medications at baseline are defined as the ARV medications taken on or up to 2 day prior to first dose date of study drug.

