- 6) Screen failure participants are the participants who were screened and answered “No” for any inclusion criteria or “Yes” for any exclusion criteria regardless of which version of protocol the participant was consent to, or participants who have missing answer to any inclusion or exclusion criteria.

- 7) Baseline ARV medication is defined as:

Using the ARV raw dataset, include all prior ARVs (where ARV.CMSCAT = “Prior ARV”), taken on or up to 2 day prior to first dose date (or randomization date if not treated), i.e. End date of ARV \geq first dose date - 2.

- 8) For last dose date calculation:

- For participants who receive injection or infusion, the last dose date is defined as the latest nonmissing end date of the study drug used.
- For participants who do not receive injection or infusion, the last dose date is defined as the last dose date of oral LEN.
- If the date of last dose is incomplete or missing (eg, due to lost to follow-up), the latest nonmissing study drug start dates the clinic visit dates, and the laboratory visit dates excluding the dates of any follow-up visits will be used to impute the last dose date.

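### Background ART that was never stopped has no restart date, so the Week 26 snapshot and Per Protocol rules would credit its suppression to the study regimen

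*SAP*

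**What the plan says.** - **Requirement.** Protocol 3.3 has every participant stop background oral ARVs one day before Day 1. Protocol Table 5-2 lists as prohibited "Any ARV not part of the study treatment regimen".
- **Snapshot.** SAP 6.1.2 and Appendix 2 use HIV-1 RNA "up to the earliest date of (196 days [28 weeks] after the dose date of complete long acting regimen, date of restarting ART"). SAP 3.8.1 defines the ART restart date as the date on which ART is resumed. Success is a last on-treatment value below 50 copies/mL in the Day 176 to 224 window, with no condition on ARV use.
- **Full Analysis Set (SAP 3.1.2).** It requires the complete long-acting regimen. The only protocol violation that excludes a participant is chronic hepatitis B.
- **Per Protocol set (SAP 3.1.3).** It applies the same data cut. Its exclusions are no on-treatment Week 26 RNA (unless due to discontinuation for lack of efficacy), partial or missed study doses, prior anti-HIV-1 antibodies, and immunosuppressants or chemotherapy. Nonstudy ARV use is not among them.
- **Nonstudy ARVs (SAP 7.4.1).** "Any nonstudy drug ARV medications used prior to, during, or after the study (if collected) will be listed". Baseline ARVs are also summarized. No efficacy rule refers to either output.

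**The concern.** HIV-1 RNA at Week 26 is evidence about lenacapavir plus the two antibodies only if nothing else is suppressing the virus. The SAP accepts this, because it discards RNA from the date ART is restarted. That guard depends on a stop followed by a resumption. If background ART simply continues past Day 1, nothing is resumed and the guard has no date to act on.

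The Per Protocol set is where one would expect such a case to be removed. It already excludes for immunosuppressants and prior antibodies, but not for the drug class that acts directly on the endpoint. If continued ART keeps the participant suppressed, the error runs one way, towards a higher response rate in both the main and the supportive analysis.

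**Working it through.** **1. Follow one participant through the rules.** Suppose background ART is not stopped, all study drugs are given on Day 1, and RNA is below 50 at the Week 26 visit.

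| Rule | Effect on this participant |
|---|---|
| Full Analysis Set (SAP 3.1.2) | Included |
| Restart cut (SAP 3.8.1, 6.1.2) | Does not act: nothing was resumed |
| 196-day cap (SAP 6.1.2) | Does not act: the visit is nominally Day 182, ± 3 days, before the cap |
| Snapshot category (SAP 6.1.2) | HIV-1 RNA < 50 |
| Per Protocol exclusions (SAP 3.1.3) | None applies; retained as < 50 |
| M = F and M = E (SAP 6.2.2.1) | Address missing values only; counted as < 50 |
| Important deviations (SAP 4.3) | May be summarized and listed; no effect on the efficacy result |

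The restart date is therefore the only ARV-triggered cut, and it misses this case.

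**2. Reproduce the plan's own figures.** Inputs from Protocol 8.10 and SAP 1.3: n = 20, assumed rate 95%, bound 83%, one-sided exact α = 0.025.

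- Requiring 20/20: α = 0.83^20 = 0.0241; power = 0.95^20 = 0.358. This matches the stated power of at least 35%.
- Allowing 19/20: α = 0.123, which is too large. Only 20/20 meets the planning criterion.
- The plan's failure-rate table gives upper limits of 16.8% for 0 events and 24.9% for 1 event. The response lower bounds are therefore 100 − 16.8 = 83.2% and 100 − 24.9 = 75.1%.

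**3. Illustrate with one participant.** The documents give no count, so one is assumed. All 20 are recorded as suppressed.

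| Handling | Result | Exact 95% lower bound |
|---|---|---|
| As written: counted < 50 | 20/20 | 0.025^(1/20) = 83.2% |
| Not counted as < 50 | 19/20 | 75.1% |
| Excluded | 19/19 | 0.025^(1/19) = 82.4% |

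One participant carries 1/20 = 5 points overall and, with 1:1 allocation, about 1/10 = 10 points in a group. In a group of 10, the lower bound is 69.2% for 10/10 and 55.5% for 9/10.

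**4. Average effect.** Reclassifying a participant is not the same as bias, because that person might have stayed suppressed on the study regimen alone. Assume continued ART always suppresses, and one of 20 is on it.

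- True rate 95%: expected rate (19 × 0.95 + 1)/20 = 95.25%, up 0.25 points. Chance of 20/20 rises from 35.8% to 0.95^19 = 37.7%.
- True rate 83%: expected rate (19 × 0.83 + 1)/20 = 83.85%, up 0.85 points. Chance of 20/20 rises from 2.41% to 0.83^19 = 2.90%.

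**The case against.** The strongest reply is that this is a protocol deviation that would be seen. Stopping ART is mandatory, other ARVs are prohibited, concomitant medications are reviewed at every visit (Protocol Appendix 2), disallowed use must be reported to the sponsor (Protocol 5.4), and ARVs are listed by participant. In about 20 people a reader could find a case. Efficacy is secondary, and the number of cases may be zero. All of this stands and limits the size of the point. It does not close it, because visibility in a listing leaves the snapshot and Per Protocol results unchanged.

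A reader might infer more than the documents support:

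- **That SAP 7.4.1 anticipates prohibited use.** Its reference to use during the study covers ART resumed at Week 26 or after virologic failure, both of which are planned while follow-up runs to Week 52.
- **That SAP 3 keeps all snapshot data when no restart is recorded.** The sentence "For participants who did not restart ART on or before last study date or have missing ARV restart date, all data will be included" belongs to the LA Regimen Period Analysis, and SAP 6 takes the snapshot endpoints out of that framework. The snapshot gap rests on SAP 6.1.2 and 3.8.1 alone.
- **That the baseline-ARV definition does harm.** Appendix 5 item 7 takes prior ARVs "taken on or up to 2 day prior to first dose date (or randomization date if not treated") and sets no upper limit on the end date. It feeds a baseline summary, is filtered to records categorized as prior ARV, and touches no efficacy rule.
- **That injectable ART is a second route.** Inclusion 4 says only "On first-line ART for ≥ 2 years prior to screening", but the synopsis and Protocol 3.2 define the population as suppressed on oral ART, and Protocol 3.3 says "all participants will resume their baseline regimen of once daily oral ART". The documents mention no participant on an injectable regimen.
- **That one case would reverse the trial's conclusion.** The 83% bound appears only in the sample-size rationale, and the SAP plans no test against it.

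**Conclusion.** The gap is real and narrow. Applied as written, the SAP counts a participant suppressed by ART that was never stopped as HIV-1 RNA < 50 in both the Full Analysis Set and the Per Protocol analysis. Under the stated assumption that such ART suppresses, the error can only raise the response rate.

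Each affected participant carries 5 points of 20. If that person would have failed without ART, the true picture is 19/20 (lower bound 75.1%) reported as 20/20 (83.2%). Averaged over whether they would have failed, one case adds 0.25 points at a true rate of 95% and 0.85 points at 83%. How many cases exist cannot be read from the documents, and zero is possible. The comparisons with 83% illustrate sensitivity at n = 20; they do not show that a planned decision would change.

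**What to change.** 1. **Per Protocol set (SAP 3.1.3).** Add an exclusion for participants who took any nonstudy ARV after Study Day 1 and before the Week 26 HIV-1 RNA used in the analysis, other than ART restarted per protocol at Week 26 or for virologic failure. The exception is needed because every participant is due to resume ART at Week 26. Without it, the criterion could empty the set.
2. **Minimum overlap.** Prespecify how much use counts as sustained, so that an isolated dose near Day 1 does not exclude a participant who was then off ART for about 25 weeks.
3. **Sensitivity analysis (SAP 6.1.3).** Repeat the Week 26 snapshot with HIV-1 RNA obtained during such sustained overlap not counted as < 50.
4. **Leave the primary snapshot rule unchanged.**

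Both additions can be derived from the ARV dataset that SAP Appendix 5 item 7 already uses, assuming on-study start and stop dates were captured (SAP 7.4.1 is conditional on collection). The Primary Cohort's Week 26 analysis is complete, so this applies to the final analysis. If the SAP is already final, SAP 1 provides for documenting the change in the clinical study report.

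The cost is a few lines of text and one derivation. The downside is that the Per Protocol set or the sensitivity response rate may fall slightly if an overlap is found. If none is found, the results do not change and the report can say so.

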7.4.2. Prior and Concomitant Non-ARV Medications

Concomitant non-ARV medications are defined as non-ARV medications taken while a participant took study drug. Use of concomitant medications from Study Day 1 up to the last exposure date, will be summarized (number and percentage of participants) by treatment group and total, and by preferred name. Multiple drug use (by preferred name) will be counted only once per participant. The summary will be sorted alphabetically by preferred drug name. For drugs with the same frequency, sorting will be done alphabetically.

If the start or stop date of non-ARV medications is incomplete, the month and year (or year alone, if month is not recorded) of the start or stop date will be used to determine whether the non-ARVs are concomitant or not. The medication is concomitant if the month and year of the start or stop (or year of the start or stop, if month is not recorded) of the medication does not meet either of the following criteria:

The month and year of stop of the medication is before the first dose date of study drug

If the start and stop date of non-ARV medications are complete, the start date is not after last exposure date and the stop date is not before first dose date, or the non-ARV medications are marked as ongoing and start date is on or before last exposure date, the non-ARV medications are concomitant.

Summaries of non-ARV concomitant medications will be based on the Safety Analysis Set. No formal statistical testing is planned. A by-participant listing for all non-ARV concomitant medications including prior medication will be listed and sorted by participant ID number and administration date in chronological order.

7.5. Electrocardiogram Results

The investigators' assessment of ECG results are collected.

A shift table of the investigators' assessment of ECG results at each scheduled postbaseline visit compared with baseline values will be presented by treatment group using the following categories: normal; abnormal, not clinically significant; abnormal, clinically significant; or missing. The number and percentage of participants in each cross-classification group of the shift table will be presented. Participants with a missing value at baseline or postbaseline will not be included in the denominator for percentage calculation. No inferential statistics will be provided.

A by-participant listing for ECG assessment results will be provided by participant ID number and visits in chronological order.

